5.4 Study Endpoints

5.4.1 Primary Endpoints

5.4.1.1 Primary Safety Endpoint

The primary safety endpoint of the study is **combined safety** at 30 days, defined according to modified VARC-2¹ ("TAVI early safety") as the composite of:

- All-cause mortality
- All stroke (disabling and non-disabling)
- Life-threatening or disabling bleeding
- Acute kidney injury – Stage 2 or 3 (including renal replacement therapy)
- Coronary artery obstruction requiring intervention

- Major vascular complication
- Valve-related dysfunction requiring repeat procedure (BAV, TAVI, or SAVR)

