12-lead ECG ³	X		X		
Concomitant Medications	X	X	X	X	
Pregnancy Test ⁴	X				
Hematology/Chemistry ⁵	X		X		
Cardiac Enzymes ⁶	X ⁶		X ⁶		
CT Imaging ⁷	X				
Cerebral DW-MRI ⁸			X		
NIH Stroke Scale ⁹	X		X	X	
Modified Rankin Scale ⁹	X		X	X	
TAVI		X			
Echocardiography (SOC) ¹⁰			X		
Device deployment		X			
Adverse Events		X	X	X	
Phone call to assess mortality/ Stroke					X

¹ Physical examination to include heart rate, blood pressure, and ischemic/anginal status (CCS or silent ischemia). The screening/baseline assessment must also include NYHA functional capacity, height, and weight.

² If the full screening/baseline review of eligibility criteria is conducted before the day of enrollment, the following repeat review of selected eligibility criteria should be performed on the day of enrollment and randomization (§6.2.1) to confirm study eligibility, using the most recent available laboratory values and clinical assessments: 1) Ensure that the subject has not had symptoms or chemistry results indicating acute myocardial infarction (§6.1.2.1.5); 2) Ensure that the most recent eGFR remains ≥ 30 (§6.1.2.1.10); 3) Ensure that there are no signs of cardiogenic shock (§6.1.2.1.13); and 4) Review the planned approach for TAVI, as certain approaches will make the subject ineligible for the study (§6.1.2.1.1).

³ Screening/baseline ECG may be performed up to 30 days prior to procedure, as long as there have been no intervening signs or symptoms of myocardial ischemia (in which case the ECG should be performed within 24 hours prior to enrollment). The post-procedure ECG must be performed within 24 hours of the procedure or prior to hospital discharge (whichever occurs first).

⁴ Female patients of childbearing potential must have a pregnancy test within 14 days prior to the procedure

⁵ Hematology and chemistry within 14 days prior to the procedure are defined in §7.2.

⁶ For the screening/baseline assessment, cardiac enzymes (CK), isoenzymes CK-MB or troponins obtained up to 14 days prior to the procedure (or on current admission) are acceptable, provided there has been no intervening episode of myocardial ischemia (in which case cardiac enzymes should be confirmed within 24 hours prior to enrollment). Post-procedure CK/CKMB or troponin (preferably CKMB isoenzyme) will be measured post procedure when clinically indicated. If cardiac biomarkers are elevated, they should be repeated per local standard of care.

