7.6 One-month Follow-up (Clinic Visit)

All subjects will return to the clinic at 30 days (± 7 days) post-procedure for a clinical evaluation.

The 30 day follow-up visit will consist of the following assessments:

- Physical examination
- Documentation of any adverse events/ serious adverse events occurring since the previous evaluation
- Current concomitant medication documentation, including antiplatelet and anticoagulant therapy
- NIH Stroke Scale (NIHSS): Neurologic status evaluation using the NIH stroke scale must be performed by a neurologist or a clinical designee (e.g. neurology fellow).
- Modified Rankin Scale (mRS) must be performed by a neurologist or a clinical designee (e.g. neurology fellow).

- A full neurological evaluation should be performed by a neurologist in all patients in whom a stroke or TIA is suspected on the basis of the NIHSS, mRS, or other signs or symptoms.
- A neuropsychological test battery (§16.7), to be administered by a qualified individual. The test battery includes: (Phase I only)
 - Montreal Cognitive Assessment (MoCA)
 - Repeatable Battery for the Assessment of Neuropsychological Status (RBANS)
 - Trail Making Test Parts A and B
- The Short Form 36 Health Survey (SF-36) (Phase I only)

Prior to concluding the visit, research staff should also review the follow-up requirements with the subject to help ensure that the patient can be contacted by telephone at the three-month follow-up time point.

Note: All clinically significant adverse events should be carefully documented by the research staff using the adverse event data forms. Any clinically-indicated neuroimaging should be forwarded to the MRI Core Laboratory.

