7.7 Three-month Follow-up

7.7.1 Phase I:

All subjects in Phase I were expected to return to the clinic at 90 days (\pm 14 days) post-procedure for a clinical evaluation.

The 90 day follow-up visit consisted of the following assessments:

- Physical examination including ischemic / anginal status (CCS or silent ischemia), heart rate, and blood pressure
- Frailty assessment with the Clinical Frailty Scale
- Documentation of any adverse events/ serious adverse events occurring since the previous evaluation
- Current concomitant medication documentation, including antiplatelet and anticoagulant therapy
- NIH Stroke Scale (NIHSS): Neurologic status evaluation using the NIH stroke scale must be performed by a neurologist or a clinical designee (e.g. neurology fellow).
- Modified Rankin Scale (mRS) must be performed by a neurologist or a clinical designee (e.g. neurology fellow).
- A full neurological evaluation should be performed by a neurologist in all patients in whom a stroke or TIA is suspected on the basis of the NIHSS, mRS, or other signs or symptoms.
- A neuropsychological test battery (§16.7), to be administered by a qualified individual. The test battery includes:
 - Montreal Cognitive Assessment (MoCA)
 - Repeatable Battery for the Assessment of Neuropsychological Status (RBANS)
 - Trail Making Test Parts A and B

- The Short Form 36 Health Survey (SF-36)

Note: All clinically significant adverse events should be carefully documented by the research staff using the adverse event data forms. Any clinically-indicated neuroimaging should be forwarded to the MRI Core Laboratory.

7.7.2 Phase II:

In Phase II, a telephone contact at 90 days (\pm 14 days) post-procedure will establish:

- Mortality
- Stroke

If death or stroke is reported, source documentation will be requested from treating facility to enable CEC adjudication of cause of death (cardiovascular [subclassified and neurologic-event related] or non-cardiovascular) and stroke classification according to the protocol-specified definitions.

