9.9 Reporting

9.9.1 General Adverse Event Reporting Procedures

Investigators are required to keep records on “all relevant observations, including records concerning adverse device effects (whether anticipated or unanticipated)” according to 21 CFR 812.140. Adverse event collection will occur from the point of study enrollment to study closure. All new or worsening (from baseline) clinically significant adverse events will be captured on the AE CRF through the 90-day follow-up telephone visit. Non-clinically-significant adverse events will not be required post discharge from the initial study procedure. It is the responsibility of the Investigator to assess the subject for adverse events and, if it is determined that a clinically significant AE has occurred, to capture the required adverse event information on the AE CRF. Independent monitoring will be conducted (§14.1) to review source documentation and verify the complete and accurate capturing of adverse events.

The general procedure for investigators reporting any adverse event is as follows:

- If an adverse event occurs, complete all sections of the Adverse Event CRF
- Each unique event/diagnosis must be documented separately
- Documented pre-existing conditions are not considered to be reportable AEs unless there is a change in the nature or severity of the condition
- The AE CRF must be reviewed by the investigator

For adverse events not meeting the criteria for an SAE or (potential) UADE, the sponsor recommends that the Investigator notify the sponsor within 10 working days of first learning of the AE using the electronic data capture (EDC) CRF. If necessary, the Investigator may be requested to provide de-identified copies of source documentation (e.g., physician/nurse notes or summaries) regarding the event.

The Investigator must also notify the responsible IRB/EC regarding new and significant safety information and any events identified by Keystone Heart Ltd. that require expedited FDA or other regulatory authority reporting as serious, unexpected, and related to the investigational device. It is the responsibility of the investigator to ensure site-specific IRB/EC reporting requirement are met.

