12.4.2 Primary Safety Endpoint

The primary safety hypothesis is that the rate of the Combined Safety Endpoint (defined according to VARC 2 as the composite of death, stroke, life-threatening or disabling bleeding, AKI [Stage 2/3], coronary artery obstruction requiring intervention, major vascular complication, and valve-related dysfunction requiring repeat procedure) at 30 days in the group undergoing TAVI with the TriGuard HDH or TriGUARD 3 system (Intervention group) is significantly less than the Performance Goal (PG). The following analysis will be carried out in the AT (primary analysis population) and ITT populations including Roll-ins.

The primary safety analysis will assess if the Intervention group's safety endpoint rate is significantly less than 34.4% using a one-sample z-test of proportions. Specifically, the null and alternative hypotheses to be tested are:

$$H_0: \pi \geq 0.344$$

$$H_1: \pi < 0.344$$

where π is the true, unknown, safety event rate for the Intervention arm.

The number and percentage of patients in each group experiencing the safety endpoint rate will be presented for each treatment; in addition, one-sided 95% confidence intervals of the percentage will be presented, based on the normal approximation to the binomial distribution. For the intervention group, the above null hypothesis will be carried out at a one-sided 0.05 level of significance using the one-sample z-test of proportions. Only AT and ITT patients who experienced a safety endpoint or had at least 23 days (30 days minus the allowable 7 day visit window) of follow-up will be included in the analyses.

As a secondary analysis, to account for any missing data in the primary endpoint (caused by not experiencing the safety endpoint AND prematurely withdrawing from the study before 23 days of follow-up), a tipping point analysis will be conducted. Here the above safety null hypothesis will be repeatedly tested, first assuming 0 patients with missing data failed (i.e., experienced the safety event), then assuming 1 patient with missing data experienced the safety event, then assuming 2 patients with missing data experienced the safety event, etc. Of interest is the "tipping" point, i.e., the number of Intervention missing data subjects who must be imputed as failures in order for the safety null hypothesis to no longer be rejected.

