12.4.9 Additional Analyses

The following data will be summarized using descriptive statistics presented by treatment group:

- Subject enrollment and data compliance by site and visit (data compliance at each visit is percent of patients whose data forms have been collected and entered divided by the percent of patients whose forms should have been collected and entered) (ITT, eITT, PT, and AT populations)
- Frequency (number and percent of patients) with each type of concomitant medication (AT population)
- Frequency (number and percent of patients) with each site-reported Treatment Emergent AE overall and by MedDRA system organ class and preferred term (a treatment emergent AE is an AE that started or worsened during or after the index procedure) (AT population)
- Frequency (number and percent of patients) with each site-reported Treatment Emergent Serious AE overall and by MedDRA system organ class and preferred term (AT population)
- Frequency (number and percent of patients) with each site-reported Treatment Emergent AE or SAE, by CEC-adjudicated relationship to the investigational device or procedure (AT population)
- Protocol deviations (number and percentage of patients with each deviation type) (ITT population)
- Kaplan-Meier plots for MACCE and TAVI early safety through 30 days (AT Population; patients without an event will be censored at 30 days or day of withdrawal, whichever is earlier)
- Detailed listings on primary and secondary endpoints, site-reported AE as well as protocol deviations

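### Phase II primary safety: 23 days of follow-up counts as event-free at 30 days, and the text conflicts on whether the later call asks about events other than death and stroke

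*Combined protocol and SAP*

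**What the plan says.** - **Endpoint.** Section 5.4.1.1: "The primary safety endpoint of the study is combined safety at 30 days". The components are death, stroke, life-threatening or disabling bleeding, stage 2 or 3 acute kidney injury (AKI), coronary obstruction requiring intervention, major vascular complication and valve dysfunction requiring a repeat procedure.
- **Who is analysed.** Section 12.4.2 includes subjects who had an endpoint event, or who "had at least 23 days (30 days minus the allowable 7 day visit window) of follow-up will be included in the analyses".
- **What counts as missing.** The tipping-point analysis in the same section covers event-free subjects "prematurely withdrawing from the study before 23 days of follow-up".
- **The visit.** Section 7.6: "All subjects will return to the clinic at 30 days", with a window of 7 days either side. Adverse events are recorded back to the previous evaluation.
- **After that visit, Phase II.** Table 7a has a 90-day row reading "Phone call to assess mortality/ Stroke" and no Adverse Events mark in that column. Section 7.7.2 lists mortality and stroke as what the call establishes, and adds: "If death or stroke is reported, source documentation will be requested from treating facility".
- **The other instruction.** Section 9.9.1 says that new or worsening "clinically significant adverse events will be captured on the AE CRF through the 90-day follow-up telephone visit". Section 9.9.2 makes any event that may meet endpoint criteria reportable as a serious adverse event (SAE).

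**The concern.** A visit on day 23 is in window and completes the subject's safety follow-up. If that subject has a life-threatening bleed on day 27, it is a 30-day endpoint event, yet neither the visit nor the call as scripted in Section 7.7.2 asks about it. If the site does not hear of it by another route, the subject is analysed as event-free, and no planned sensitivity analysis reaches the case. The Kaplan-Meier rule in Section 12.4.9 also carries event-free subjects to day 30 unless they withdrew.

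The direction matters because the test is single-arm against a fixed goal. There is no control arm in which the same losses could cancel, so every missed event favours passing. Section 12.2.1 makes meeting this endpoint a condition of trial success.

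**Working it through.** **1. The plan's own figures.** Inputs from Sections 12.2.1 and 12.2.4: goal p0 = 0.344, expected rate p1 = 0.25, n = 179, one-sided alpha 0.05, one-sample z-test.
- Critical rate = p0 - 1.645 × √(p0(1 - p0)/n) = 0.344 - 1.645 × √(0.344 × 0.656/179) = 0.2856. The largest passing count is 51, since 51/179 = 28.49% and 52/179 = 29.05%. This matches the stated 28.5%.
- Power = Φ[((p0 - p1)√n - 1.645√(p0(1 - p0)))/√(p1(1 - p1))] = 86.4%, or 84.5% with a continuity correction, against 85% stated.

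The sample-size figures stand. The point is about ascertainment.

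**2. Which components are exposed.**
- Death and stroke: not exposed, because the 90-day call asks about both.
- AKI: not exposed. Appendix I defines it by creatinine change up to 7 days, so a new kidney event in days 24-30 is outside the endpoint.
- Bleeding, major vascular complication, coronary obstruction requiring intervention, repeat valve procedure: exposed.

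**3. Which subjects are exposed.** Only Phase II subjects whose 30-day visit falls on days 23-29. From day 30 on, the visit itself covers the endpoint period. Phase I had a 90-day clinic visit at which adverse events were recorded (Section 7.7.1).

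**4. Size, by illustration only.** The documents give neither the share of events falling in days 24-30 nor the spread of visit days. Assume:
- f = share of 30-day endpoint events with onset in days 24-30: 2%, 5% or 10%;
- visit days spread evenly over days 23-37. The mean unobserved part of the last week is then (1/14) × ∫ from 23 to 30 of (30 - v)/7 dv = 3.5/14 = 0.25;
- no unvisited event reported by any other route.

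Loss m = 0.344 × f × 0.25. The chance of passing when the true rate equals the goal is the exact binomial P(X ≤ 51 | n = 179, p = 0.344 - m).

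| f | m (points) | subjects (179 × m) | chance of passing |
|---|---|---|---|
| none | 0 | 0 | 5.5% |
| 2% | 0.17 | 0.3 | 6.0% |
| 5% | 0.43 | 0.8 | 6.9% |
| 10% | 0.86 | 1.5 | 8.7% |

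The 5.5% in the first row exceeds the nominal 5% because the z-test is approximate.

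For a given f and visit spread, these rows are upper bounds: the loss is applied to the whole composite although three of its components are not exposed, and spontaneous reporting is set to nil. They are not bounds on the visit spread. If every visit fell on day 23, f = 5% would give m = 1.72 points and 13.2%, but nothing in the documents suggests that pattern.

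**The case against.** The strongest reply is that the 23-day rule does not cut off event counting. It decides only which event-free subjects are evaluable, and a day-27 bleed that is reported counts. Section 9.9.1 runs adverse event collection from enrollment to study closure. Sections 9.9.2 and 11.2 make every potential endpoint event an SAE, with notification to the sponsor recommended within 3 working days of the investigator learning of it. That duty is not tied to a visit.

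This stands in part. It rules out saying that such events go uncollected by design. It does not close the gap, because the duty starts when the investigator learns of the event and the events committee adjudicates site-reported events. A bleed treated at another hospital may not reach the site if the call asks only about death and stroke. Section 9.9.1 itself speaks of a telephone visit, which fits Phase II only, so the conflict with Section 7.7.2 and Table 7a is current.

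Three stronger readings are tempting and are not supported:
- A reader might infer that late kidney events are lost too. The 7-day AKI definition rules that out.
- A reader might infer that adverse event tables set 90 days of Phase I control experience against about 30 days of TriGUARD 3 experience. Section 12.4.3 specifies pooling of controls for the primary efficacy endpoint. Section 12.4.9, which defines treatment emergence as "a treatment emergent AE is an AE that started or worsened during or after the index procedure" with no end date, does not say that these tables pool controls across phases.
- A reader might infer that the visit window must start at day 30. That is a debatable trade-off, since it would make the Phase II window differ from Phase I, whose controls may be pooled for efficacy. The gap can be closed without it.

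**Conclusion.** The point holds in a narrow form. For Phase II subjects seen on days 23-29, four components of the primary safety endpoint have no assured ascertainment to day 30. The passages on the 90-day call contradict each other, and the tipping-point analysis does not reach these subjects. Any resulting bias favours meeting the 34.4% goal.

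Its size cannot be derived from the documents and is probably small. On the assumptions above (2-10% of events late, visits evenly spread, no spontaneous reporting), about 0.3 to 1.5 subjects in 179 would be misclassified, and the chance of passing at the goal would go from 5.5% to between 6.0% and 8.7%. The repair is worth making because the error runs in one direction on a co-primary endpoint and costs little to remove.

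**What to change.** 1. Reconcile Table 7a, Section 7.7.2 and Section 9.9.1 so that all three say the same about adverse event collection after the 30-day visit in Phase II.
2. Have the existing 90-day call ask about each remaining primary safety component (bleeding, vascular, coronary, valve) with onset by day 30, and request source documents for adjudication when an answer is positive, as is already planned for death and stroke.
3. In Section 12.4.2, count a subject as event-free only if some contact covers day 30 for these components. Otherwise, add event-free subjects last assessed on days 23-29 to the tipping-point analysis alongside the withdrawals before day 23.

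The cost is protocol and SAP wording and a few extra questions on a call already scheduled. The observed safety rate may come out slightly higher. The sample size does not change.

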5.4.1.1.2 Primary Efficacy Endpoint- **Phase II**

The primary efficacy endpoint of the study is the **hierarchical composite efficacy endpoint**, determined by pair-wise comparisons among all subjects according to the following pre-specified hierarchy of adverse outcomes:

- All-cause mortality and/or any stroke (fatal and non-fatal, disabling or non-disabling) [evaluated at 30 days]
 - If both had a death/stroke, a time to event analysis by days will determine a win
 - If both patients had a stroke at the same day the comparison moves to the next tier
- NIHSS worsening (increase from baseline) [evaluated at 2 to 5 days post-procedure]
- Freedom from any cerebral ischemic lesions detected by diffusion-weighted magnetic resonance imaging (DW-MRI) 2 to 5 days post-procedure
- Total volume of cerebral ischemic lesions detected by diffusion-weighted magnetic resonance imaging (DW-MRI) 2 to 5 days post-procedure.

Each subject in the intervention group will be compared with each and every subject from the control group based on the above hierarchy according to the Finkelstein-Schoenfeld method.² For example, if Subject A dies or has stroke and Subject B survives free of stroke to 30 days, Subject B wins (score +1) and Subject A loses (score -1). If both subjects die or both have a stroke on the same day, it is equilibrium (score 0). If both subjects survive free of stroke to 30 days, the comparison moves to the next tier of the hierarchy. A lack of an event is given a +1 score. An event which is less severe than the comparison gets a 0 score (for example death vs. stroke)

After all between-subject comparisons have been performed, scores are summed to obtain a cumulative score for each subject, and outcomes between treatment groups are then compared.

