In addition, in the final analysis, assessments of study-center and of region effect on the primary safety endpoint will be carried out on the interventional group within the AT population using logistic regressions. A 0.15 level of significance will be used to assess the significance of each of the study center and region effects on the safety endpoint. A non-significant result for each of study centers and regions will support the pooling of patients across study centers and across regions for the primary safety analysis. A significant result will require further inspection of the by-center and by-region results to assess if poolability is appropriate. Note that centers with less than 5 subjects will be pooled with other centers by closest geographic region; this pooling will be carried out prior to the unblinding.

In addition, a logistic regression to assess the consistency of the primary safety endpoint rate across the following categories will also be performed on the interventional arm (separately for Phase I and Phase II) within the AT population:

- Subject gender (male versus female)
- Valve prosthesis type (Edwards vs. Medtronic)

- Operative risk (by Society of Thoracic Surgeons [STS] Risk Score)
- Type and duration of antiplatelet therapy:
 - Pre- and peri-procedural therapy:
 - Protocol-recommended antiplatelet therapy vs. other
 - Maintenance therapy:
 - Dual antiplatelet therapy (DAPT) to 90 days vs.
 - Monotherapy (aspirin or clopidogrel) to 90 days vs.
 - Warfarin with antiplatelet therapy to 90 days vs.
 - Other

As above, a 0.15 level of significance will be used to assess the significance of the difference of the primary safety endpoint rate across the subgroups of each factor.

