In the final analysis, assessment of treatment-by-study-center and treatment-by-region on the primary efficacy endpoint will be carried out on the eITT population using quantile regression. Total score obtained for each subject using the proposed approach (Finkelstein and Schoenfeld) will be the model dependent variable. The following two models will be built: 1.) Model inclusive of treatment, study center, and treatment-by-study center interaction, and 2.) Treatment region (US versus OUS, Phase I only), and treatment-by-region interaction. A 0.15 level of significance will be used to assess the significance of each of the study center and region effects on the efficacy endpoint. A non-significant result for each of study center and region will support the pooling of patients across study centers and across regions for the primary efficacy analysis. A significant result will require further inspection of the by-center and by-region results to assess if poolability is appropriate. Note that centers with less than 5 subjects will be pooled with other centers by closest geographic region; this pooling will be carried out prior to the unblinding.

Additionally, an assessment of treatment-by-study-center and treatment-by-region on each component of the primary efficacy endpoint will be carried out on the eITT population using analysis of variance on the cube root transformation for total lesion volume data and logistic regression for death/stroke and NIHSS worsening, with effects for 1.) Treatment, study center, and treatment-by-study center interaction, and 2.) Treatment, region (US versus OUS, Phase I only), and treatment-by-region interaction. As above, a 0.15 level of significance will be used to assess the significance of the interaction; a non-significant interaction or an interaction that is significant but only quantitative (and not qualitative) in nature will support the pooling of patients across study centers and across regions for the primary analysis; and centers with less than 5 subjects will be pooled with other centers by closest geographic region, with pooling carried out prior to the unblinding.

In addition, the above analysis will be repeated in the eITT population (separately in Phase I and Phase II analysis sets) to assess the consistency of treatment effects on each component of the primary efficacy endpoint across the following variables:

- Subject gender (male versus female)
- Valve prosthesis type (Edwards vs. Medtronic)

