- Operative risk (by Society of Thoracic Surgeons [STS] Risk Score)
- Type and duration of antiplatelet therapy:
 - Pre- and peri-procedural therapy:
 - Protocol-recommended antiplatelet therapy vs. other
 - Maintenance therapy:
 - Dual antiplatelet therapy (DAPT) to 90 days vs.
 - Monotherapy (aspirin or clopidogrel) to 90 days vs.
 - Warfarin with antiplatelet therapy to 90 days vs.
 - Other

As above, analysis of variance on the cube root transformation for total lesion volume data and logistic regression for death/stroke and NIHSS worsening will be used, and a 0.15 level of significance will be used to assess the significance of the interaction.

If the primary efficacy endpoint is met in the primary (eITT) analysis population, sequential testing of the primary efficacy hypothesis will be conducted in the ITT analysis population of evaluable subjects (Roll-In patients are excluded.) As a secondary analysis, the primary efficacy endpoint and its components will be evaluated in the ITT analysis population of evaluable subjects (Roll-In patients are excluded). As an additional analysis, the primary efficacy endpoint will be evaluated in the PT population of subjects with available data.

An additional analysis of the primary efficacy endpoint will also be performed in the primary eITT analysis population with adjustment for pre-existing cerebral lesion volumes. The adjustment will be performed using a quantile regression with the resultant score being the dependent variable and group and the pre-existing cerebral lesion volumes will be independent. Specifically, the PROC QUANTREG procedure will be used to model the median of the score with QUANTILE=0.5 option.

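### The 12.4.2 consistency analysis groups subjects by antiplatelet regimen held to day 90, which is settled after the 30-day safety outcome, partly by it, and is not recorded in Phase II

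*Combined protocol and SAP*

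**What the plan says.** **Safety, section 12.4.2.** After the primary test against the performance goal, logistic regression in the intervention arm of the As Treated population, separately by phase, examines the safety rate across several factors. One is the type and duration of antiplatelet therapy. Its maintenance part has four classes: "Dual antiplatelet therapy (DAPT) to 90 days vs" single-agent therapy to 90 days, warfarin with antiplatelet therapy to 90 days, and Other. The criterion is a main effect: "a 0.15 level of significance will be used to assess the significance of the difference of the primary safety endpoint rate across the subgroups".

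The outcome is earlier than the grouping: "The primary safety endpoint of the study is combined safety at 30 days" (5.4.1.1). Section 12.4.2 keeps every subject who had a safety event, however early, so early deaths stay in the analysis. No rule says where a subject belongs who dies or changes regimen before day 90.

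**Efficacy, section 12.4.3.** The same classes recur (for example "Monotherapy (aspirin or clopidogrel) to 90 days vs" the others). The purpose here is "to assess the consistency of treatment effects on each component of the primary efficacy endpoint across the following variables", and "a 0.15 level of significance will be used to assess the significance of the interaction".

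**Data.** Table 7 (Phase I) schedules concomitant medications at day 90. Table 7a (Phase II) does not, and the Phase II day-90 telephone contact in 7.7.2 establishes mortality and stroke only.

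**The concern.** A factor used to ask whether an outcome differs between groups should be settled before the outcome, or at least not be changed by it. Here the order is reversed. Completing 90 days on a regimen requires surviving 90 days, so on a literal reading the three named classes contain no 30-day deaths, and Other receives deaths that are events with certainty. A bleed or stroke by day 30 may also lead to a change of regimen, which again moves a subject with an event out of the starting class.

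The result could show events clustering outside dual therapy and a test flagging a difference, even if regimen had no bearing on safety. A reader could take this artefact as evidence about antiplatelet therapy with the device. Separately, if the factor cannot be filled in Phase II, whatever replaces it will be chosen after the data are in hand.

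**Working it through.** **1. The plan's own safety figures reproduce.** With p0 = 0.344, one-sided 0.05 and n = 179, the critical rate is 0.344 − 1.645 × √(0.344 × 0.656 / 179) = 0.2856. That allows 51 events, and 51/179 = 28.5%, as stated. Power at 25% is Φ[(0.2856 − 0.25) / √(0.25 × 0.75 / 179)] = Φ(1.10) ≈ 86%, against 85% stated. Allowing 5% loss, 179/0.95 gives 189, against 190. The concern is not with these figures.

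**2. Inputs for the regimen test.**
- From the documents: 190 intervention subjects, event rate 25%, test level 0.15, and device-arm 30-day mortality in Table 11a of 1.32% (simple mean), 1.33% (weighted) and 1.6% (meta-analytic).
- Assumed: starting shares of 60% dual therapy, 15% monotherapy, 15% warfarin plus antiplatelet and 10% Other, with no effect of regimen on the outcome.

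**3. Expected class rates when only deaths move to Other.** Starting class sizes are 114, 28.5, 28.5 and 19.
- At 1.6% mortality there are 190 × 0.016 = 3.04 deaths, of which 90% (2.74) come from the named classes. Other becomes (19 × 0.25 + 2.74) / (19 + 2.74) = 7.49/21.74 = 34%. Dual therapy becomes (28.5 − 1.82) / (114 − 1.82) = 26.68/112.18 = 24%.
- At 1.3% the same steps give 6.97/21.22 = 33% and 27.02/112.52 = 24%.

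The true rate is 25% in every class.

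**4. Rejection by the likelihood-ratio test of the four-level factor at 0.15 (simulation).**

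| Grouping | Rejection |
|---|---|
| By starting regimen | about 15–16% |
| To 90 days, only deaths moved, 1.3–1.6% mortality | about 26–29% (repeat runs 25–28%) |
| As above, with event-driven switching at an assumed 4% | about 51–54% |

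In the last row, 4% of subjects have a non-fatal event that ends dual therapy. Those of them on dual therapy (0.60 × 4% = 2.4% of all subjects) move to monotherapy.

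**5. Sensitivity to the assumptions.** A second set of runs used n = 179, shares of 55/20/20/5 or 40/30/20/10, and 5–20% of event-free subjects also moving to Other by day 90. Grouping by starting regimen gave 16–18%. At 1.3% mortality, displacement by death alone gave 19–24%. If 25% of subjects with non-fatal events also changed regimen, the range was 27–92%. The direction is stable, but the size depends on change rates that the documents do not give.

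**6. The 12.4.3 interaction test.** For the binary components with 150 and 75 subjects, grouping by starting regimen rejected in 17–19%. Grouping to 90 days, with the same change rate in both arms, rejected in 17–22%. A large-sample check gave 15–16%. Change after an event that is the same in both arms shifts the odds by the same factor in both arms and leaves the interaction null. Rejection rose, to 43–57%, only when change after an event differed by arm (70% against 20%, assumed). The lesion-volume analysis of variance was not simulated.

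**The case against.** **The text does not say that deaths go to Other.** This stands in part. If each death were classed by the regimen held until death, and nobody changed regimen after an event, there would be no inflation. But the classes are worded by duration and no such rule is written.

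**A reader might infer that the outcome always decides the group.** The documents support this only for early deaths read literally. For non-fatal events the outcome can influence the class. Section 7.3 leaves antiplatelet choice to physician practice, so no switching rate can be derived.

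**A reader might use higher mortality.** At 3.2% the deaths-only rejection is about 56%, but 3.2% is the weighted control-arm mean in Table 11a and this analysis uses the intervention arm only.

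**A reader might extend the inflation to 12.4.3**, where some components are fixed by days 2–5 ("NIHSS worsening (increase from baseline) [evaluated at 2 to 5 days post-procedure"). The 0.15 level there applies to a treatment-by-regimen interaction, and step 6 shows no material inflation unless change after an event differs by arm. The plan gives no figure for that.

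**Section 7.3 asks that all medications administered be recorded.** This is a general instruction. It adds no day-90 medication review to Table 7a or to the Phase II call.

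**Nothing depends on the result.** This stands. Section 12.4.2 attaches a pooling decision only to the centre and region tests.

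**Conclusion.** The safety part of the concern holds. In 12.4.2 the maintenance factor is classified after a 30-day endpoint and partly by it, and in Phase II it cannot be built from scheduled data. With no regimen effect, and on the assumed 60/15/15/10% shares, displacement of deaths alone takes the 0.15 main-effect test from about 15% to about 26–29% at device-arm mortality of 1.3–1.6%. Event-driven switching would raise it further, to about 51–54% under the assumed 4%, a rate with no source in the documents.

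For 12.4.3 no inflated interaction test is claimed. The reason to change it is simpler: therapy to day 90 comes after the day 2–5 and day 30 components, and it is not collected in Phase II.

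This is a minor correction to a supportive analysis. The primary safety and efficacy tests are unaffected. The pre- and peri-procedural class of protocol-recommended therapy lacks a definition, but that is a separate matter of wording. Nothing here bears on which regimen patients should receive.

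**What to change.** In 12.4.2, and for the same factor in 12.4.3, replace the 90-day classes with a regimen fixed before the outcome, in one of two ways:

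- **Regimen recorded at baseline or procedure.** This is the cleaner choice. It answers a narrower question than maintenance therapy.
- **First post-procedure regimen**, with any subject who has an earlier endpoint event classed by the last regimen recorded before that event. Because dual therapy may start only after the procedure, this option needs a check that subjects with procedure-day events are not pushed into a different class by the rule itself.

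Under either option, state that deaths are classed by the regimen held before death. Regimen at discharge without such a rule is not enough: in the same model, 2–4% of subjects having an event that ends dual therapy before discharge already gives 24–41% rejection, and in-hospital deaths have no discharge regimen.

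The cost is SAP wording, settled before unblinding. Table 7a already schedules medication records at baseline, procedure, post-procedure and 30 days, so no new collection is needed.
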